B. Provide a sample size and a justification as to how you arrived at that number. If you use screening procedures to arrive at a final sample, distinguish the screening sample size from the enrolled sample size; a table may be helpful. For electronic survey studies involving online recruitment and survey completion: consider how you will set controls on how many people will join your study.

The CloudResearch initial sample will be 6,250 people, evenly divided with approximately 1,250 people in the control arm and each of the four experimental arms, respectively. This sample size will give us >80% power to detect a small effect size (d=0.12) with a conservative Bonferroni adjusted alpha of 0.0125, which was determined based on our prior research would be sufficient to see differences between all label arms. The CloudResearch sample will be broadly representative of the U.S general population, but carry the possibility of a 25% skew tolerance across demographic lines. We will recruit individuals until the target sample size has been reached by working with the managed research partner with CloudResearch.

C. Does your study meet the NIH definition of “clinical trial”: “A research study in which one or more human subjects are prospectively assigned to one or more interventions (which may include placebo or other control) to evaluate the effects of those interventions on health-related biomedical or behavioral outcomes”? If yes, the study must be listed on clinicaltrials.gov, study personnel must complete GCP training, and federally funded studies must post consent forms on approved sites, like clinicaltrials.gov.

Yes.

IV. Participants:

Describe the study participants and the population from which they will be drawn. Specify the inclusion and exclusion criteria. If you plan to include children, note their ages and whether you will include children in foster care or who are wards of the State. Note if the participants are particularly vulnerable in terms of cognitive limitations, education, legal migration status, incarceration, poverty, or some combination of factors.

A. Inclusion Criteria:

- 18 years of age or older
- Residing in the United States
- Member of the CloudResearch panel

B. Exclusion Criteria:

- Under 18 years of age
- Not residing in the United States
- Completed the survey implausibly quickly based on the distribution of the time to complete the survey among all participants

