The primary outcome measure will be the healthfulness of the fast-food meal selections, measured with a modified Nutrient Profile Index (NPI) score. NPI scores are based on the UK Ofcom Nutrient Profiling Model, which is used to score

individual foods in the U.K. to determine which ones can be marketed to children. For this study, we will generate a modified NPI score to evaluate the healthfulness of full meals comprised of multiple food items. This measure will be determined by calculating the weighted mean NPI score of all food items selected per meal, with each item's NPI score weighted by its proportionate contribution of mass in grams to the total mass of the meal. Beverages will be excluded from the modified score and assessed through secondary outcomes.

The key independent variable will be a five-category indicator of the experimental arm to which the participant is randomized. Using logistic regressions, we will explore differences in primary outcome between climate-impact label conditions (arms 2, 3, 4, and 5) vs. the QR label control, and between the label conditions (arm 2 vs. arm 3; arm 2 vs. arm 4; arm 2 vs. 5; arm 3 vs. arm 4; arm 3 vs. 5; arm 4 vs. 5).

As secondary outcomes, we will also compare total greenhouse gas emissions (kg CO₂e) associated with hypothetical orders across labeling conditions, perceived message effectiveness, total calories per meal order, and selection of a sugar-sweetened beverage within order.

5. Answer the following if they are relevant to your study design:

A. If the study has different arms, explain the process for assigning participants (intervention/control, case/control), including the sequence and timing of the assignment.

Randomization will be enabled as a function of the survey software (Qualtrics). Participants will be randomized into one of five study arms, as described above.

B. If human biospecimens (blood, urine, saliva, etc.) will be collected, provide details about who will collect the specimen, the volume (ml) and frequency of collection, how the specimen will be used, stored, identified, and disposed of when the study is over. If specimens will be collected for use in future research (beyond this study), complete the "Biospecimen Repository" section below.

N/A

C. If genetic/genomic analyses are planned, address whether the data will be contributed to a GWAS or other large dataset. Address returning unanticipated incidental genetic findings to study participants.

N/A

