Climate impact label design and fast-food meal selection

NCT06678178

Statistical Analysis Plan

Version Date: 11/05/2024

Statistical Analysis Plan

Research Question and Hypotheses:

The primary objective of this study is to test the relative effects of climate-impact menu label designs on the healthfulness of consumers' fast-food meal choices via a between subjects randomized experiment. We predict that, relative to a control label, a high impact warning label will lead to the healthiest food choices, followed by a three-level traffic-light label, then by a five-level climate impact grade, and finally a numeric carbon footprint label.

We believe the same label performance predictions will apply to our secondary outcomes, including: total greenhouse gas emissions per meal order, total calories per meal order, and selection of a sugar-sweetened beverage.

Key Variables

Primary outcome: Participants will order a hypothetical meal from an online fast-food menu via Qualtrics. Participants will be randomized to one of five label conditions that will appear on the menu: 1) a control label, 2) a high impact warning label; 3) a three-level traffic-light label, 4) a five-level climate impact grade, and 5) a numeric carbon footprint label. The primary outcome will be the healthfulness of each participant's meal selections. This score will be based on the Nutrient Profile Index (NPI) algorithm, which assigns a score from 1-100 scale based on a product's nutritional composition, with items scoring ≥ 64 considered healthy. This measure will be determined by calculating the weighted mean NPI score of all items selected per meal, with each item's NPI score weighted by its proportionate contribution of mass in grams to the total mass of the meal. Beverages will be excluded from the modified score and assessed through secondary outcomes.

Secondary outcomes: Our first secondary outcome is total greenhouse gas emissions of the hypothetical meal ordered measured in kilograms of CO₂ equivalents. This will be calculated for each menu item using nutritional and recipe information from publicly available information combined with data on associated emissions for related food items from the World Resource Institute (WRI) CoolFood Calculator. Total estimated greenhouse gas emissions per meal will be calculated as the sum of estimated emissions for all menu items ordered in a meal.

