We will use predicted margins to examine predicted mean values of each outcome for each experimental condition.

Statistically significant differences will be considered at $p<0.05$ with Bonferroni-Holm correction for multiple comparisons and all tests will be two-tailed.

We will not exclude observations based on values of any of the outcome variables. We will exclude observations of participants who complete the survey implausibly quickly based on the distribution of the time to complete the survey among all participants. We will also exclude participant who fail built-in Qualtrics survey fraud detection measures.

*This analysis plan was pre-registered on AsPredicted on 11/05/2024

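### The stated inputs (1,250 per arm, d=0.12, alpha 0.0125) give about 69% power for a two-sided comparison, not more than 80%

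*Protocol*

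**What the plan says.** Protocol Section III.B gives a total of 6,250 people, with "approximately 1,250 people in the control arm and each of the four experimental arms". It then states: "This sample size will give us >80% power to detect a small effect size (d=0.12) with a conservative Bonferroni adjusted alpha of 0.0125". The same sentence appeals to the team's prior research and says the sample is enough to separate all the label arms. The documents contain no other sample-size justification.

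Three other places bear on the calculation:

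- **Protocol Section V.C.4** lists comparisons of the primary outcome "between climate-impact label conditions (arms 2, 3, 4, and 5) vs. the QR label control", which is four tests, and then six label-versus-label comparisons.
- **SAP, Statistical Analyses** regresses the continuous primary outcome on the arm indicator and names no covariates. Significance is judged at 0.05 "with Bonferroni-Holm correction for multiple comparisons and all tests will be two-tailed".
- **SAP, Research Question and Hypotheses** predicts an order of labels ("a high impact warning label will lead to the healthiest food choices, followed by a three-level traffic-light label", and so on down to the numeric label) but gives no effect size for any of them.

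**The concern.** Sample size, effect size, alpha and power are all stated, so the claim can be checked directly. The alpha of 0.0125 equals 0.05/4, which fits the four label-versus-control tests. With 1,250 per arm, d=0.12 lies three standard errors from zero. The two-sided critical value at 0.0125 is about 2.5, which leaves too small a margin for 80% power.

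The figure matters for how the results are read. Section I of the protocol says this pilot will help choose the labels for the next study. If the power is overstated, a label with a true effect of d=0.12 will look ineffective more often than the protocol implies, and may be dropped. A null result would also be read as evidence against effects of 0.12 or more, when the sample supports that reading only from about 0.134.

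**Working it through.** **Inputs**

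- n = 1,250 per arm, equal allocation (Protocol III.B). Section IX.A says excluded participants are replaced, so 1,250 is taken as the analysed number.
- d = 0.12 and alpha = 0.0125 (Protocol III.B).
- Two-sided tests, continuous outcome, no covariates (SAP, Statistical Analyses). Protocol V.C.4 mentions logistic regression for this outcome, but d is a standardised mean difference, so the check follows the SAP's model.

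**Power at the stated inputs**

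- Noncentrality = d × √(n/2) = 0.12 × √(1250/2) = 0.12 × 25 = 3.00.
- Two-sided critical value at 0.0125 = 2.498.
- Power = Φ(3.00 − 2.498) = Φ(0.502) = 69.2%. The noncentral t distribution also gives 69.2%.

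The stated figure of more than 80% is not reproduced.

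**What the sample supports, and what the claim would need**

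- Detectable effect at 80% power = (2.498 + 0.842)/25 = 0.134.
- n per arm for d=0.12 = 2 × (2.498 + 0.842)² / 0.12² ≈ 1,549 (1,551 with the t distribution). That is about 1,550 per arm, or 5 × 1,550 = 7,750 in total.
- For 80% power with 1,250 per arm, the critical value must be at most 3.00 − 0.842 = 2.158, a two-sided alpha of about 0.031.

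**Other thresholds, same n and d**

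| Threshold | Power |
|---|---|
| Two-sided 0.0125 (Holm step 1 of 4) | 69.2% |
| Two-sided 0.0167 (step 2) | 72.7% |
| Two-sided 0.025 (step 3) | 77.6% |
| Two-sided 0.05 (step 4, or no correction) | 85.1% |
| One-sided 0.0125 | 77.6% |
| Two-sided 0.005 (0.05/10, all ten comparisons) | 57.7% |

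Among these, only two-sided 0.05 exceeds 80%. The correction may have been left out of the power calculation, but that is an inference; the documents do not show it.

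**Holm, as the SAP specifies**

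The SAP does not define the Holm family. The figures below assume the four label-versus-control tests with a shared control, two-sided family alpha 0.05, and come from 2,000,000 simulated trials. They give the power for one label at d=0.12. The effects of the other three are assumptions, because the documents give none.

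| Effects of the other three labels | Power for the label at 0.12 |
|---|---|
| 0 / 0 / 0 | 69.3% |
| 0.12 / 0.12 / 0.12 | 78.0% |
| 0.131 / 0.131 / 0.131 | 80.0% |
| 0.13 / 0.14 / 0.15 | 81.3% |
| 0.14 / 0.16 / 0.18 | 83.2% |
| 0.18 / 0.24 / 0.30 | 84.9% |

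The risk of missing d=0.12 under this family therefore runs from about 31% down to about 15%. If Holm covered all ten comparisons, the first step would be at 0.005. A 400,000-run simulation with all four labels at 0.12 then gives about 60% power for each label-versus-control test.

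**The case against.** The best defence is that Section III.B names neither the test nor its sidedness. Two-tailed testing is stated only in the SAP, dated 11/05/2024, after the protocol of 10/18/2024. Some readings do exceed 80%:

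- all four labels pooled against control at 0.0125, about 90%;
- at least one significant label when all four have d=0.12, about 92%;
- covariate adjustment explaining about 20% of the outcome variance, about 80%;
- Holm when the other labels are stronger than 0.12, as in the table.

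None of these is what the protocol describes. Pooling and any-label power cannot show differences among all label arms, which is the stated aim. No covariates are planned. Section III.B names a fixed Bonferroni alpha, and the SAP's predicted ordering carries no magnitudes. Dropping two-sidedness does not help either, since one-sided 0.0125 stops at 77.6%. The appeal to prior research may justify the choice of d, but it cannot change the power that follows from d, n and alpha.

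Two parts of the objection stand. The practical consequence is moderate: this is a pilot, and 0.134 is not far from 0.12. The comparison family is also unsettled. The protocol lists ten comparisons while 0.0125 covers four, so the 69% applies to label-versus-control tests only. Correcting for all ten would lower it.

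**Conclusion.** The power statement is wrong on its own inputs. At two-sided alpha 0.0125 with 1,250 per arm, power for d=0.12 is 69.2%, about 11 points below the 80% that the protocol says is exceeded. The detectable effect at 80% power is d=0.134.

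This rests on equal arms of 1,250 analysed participants, an unadjusted two-group comparison, and the two-tailed testing stated in the SAP. Holm can lift the power above 80%, but only under effects for the other labels that the documents do not state.

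The error is confined to the sample-size justification. Because that is the only such justification, and the correction is simple, it should be made.

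**What to change.** Replace the power sentence in Protocol Section III.B with one to this effect: for each label-versus-control comparison, 1,250 per arm gives about 69% power for d=0.12, or 80% power for d=0.134, at two-sided alpha 0.0125. Limit the closing claim about separating all label arms in the same way, because 0.0125 does not cover the six label-versus-label tests.

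If power under Holm was meant, say so, name the family of tests, and give the assumed effect for each of the four labels.

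The cost is a short text change and a less favourable number. The correction requires no change to enrolment, randomisation or the pre-registered analysis. Whether 69% at d=0.12 is acceptable is for the investigators to judge; keeping the claim as written would take about 1,550 per arm.

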Describe how you plan to ensure that the study team follows the protocol and properly records and stores study data collection forms, IRB regulatory correspondence, and other study documentation (for assistance, contact: [\[[contact]\]](mailto:[contact])).

Please provide information about study oversight to ensure compliance with IRB approval and regulatory and institutional requirements. If the study team does not follow study procedure, what is your plan for reporting protocol non-compliance?

The study team will have a shared OneDrive folder in which all study documents and protocols will be saved. The study team will have weekly meetings, and every person brought on to the study team will have an orientation meeting with [name]. [name] will be responsible for all correspondence with the IRB and all other study documentation.

C. Safety Monitoring:

1. *Describe how participant safety will be monitored as the study progresses, by whom, and how often. Will there be a medical monitor on site? If yes, who will serve in that role and what is that person's specific charge?*

Participation in this study does not pose any safety risks. The study engages participants in a very brief, 3-minute survey task that asks non-sensitive questions.

2. *If a Data Safety Monitoring Board (DSMB), or equivalent will be established, describe the following:*

- a. *The DSMB membership, affiliation and expertise.*

N/A

- b. *The charge or charter to the DSMB.*

N/A

- c. *Plans for providing DSMB reports to the IRB.*

N/A

3. *Describe plans for interim analysis and stopping rules, if any.*

N/A

D. Reporting Unanticipated Problems/Adverse Events (AEs) to the IRB (all studies must complete this section):

NOTE: The IRB does not require PROMPT reporting of all AEs, only those that are unanticipated, pose risk of harm to participants or others, and are related to the study. Anticipated AEs may be reported with the Continuing Review/Progress Report.

Describe your plan for reporting to the BSPH IRB, local IRBs, and (if applicable) to the sponsor. Include your plan for government-mandated reporting of child abuse or illegal activity.

While we do not expect any adverse events, should any occur we will report them immediately to the IRB.

E. Other IRBs/Ethics Review Boards:

*If other IRBs will review the research, provide the name of each IRB/ethics review board and its Federal Wide Assurance number, if it has one (available on [OHRP's Website](#)). For federally funded studies, subrecipients **MUST have a Federal Wide Assurance (FWA) number from the OHRP. The IRB overseeing the subrecipient should be registered with the OHRP. The BSPH IRB will not have oversight responsibility for international subrecipients, and generally will not oversee data collection at external U.S. institutions. Please contact the [BSPH IRB Office](#) with questions.***

Non-BSPH IRB/REC	FWA Number

F. “Engaged” in Human Subjects Research:

For studies that involve collaboration with non-BSPH institutions, complete the chart below by describing the collaboration and the roles and responsibilities of each partner, including the BSPH investigator. This information helps us determine what IRB oversight is required for each party. Complete the chart for all multi-collaborator studies.

Insert collaborator names and FWA numbers, if available. Note who will be “engaged” in human subjects research by filling in the following table:

	BSPH	[]	[]
For federally funded studies, collaborators' FWA	00000287	[]	[]
Primary Grant/Contract Recipient	[]	[]	[]
Grant/Contract Subrecipient	[]	[]	[]
Hiring Data Collectors	[]	[]	[]
Training Data Collectors	[]	[]	[]
Obtaining Informed Consent and/or Identifiable Data	[]	[]	[]
Accessing/Analyzing Identifiable Data	[]	[]	[]
Overseeing storage, access and use of biospecimens	[]	[]	[]

COMPLETE THE FOLLOWING SECTIONS WHEN RELEVANT TO YOUR STUDY:

XI. Secondary Data Analysis of Existing Data:

A. Study Design:

1. *Describe your study design and methods. The study design must relate to your stated aims/objectives.*

[]

2. *Provide an estimated sample size and an explanation for that number.*

[]

3. *Provide a brief data analysis plan and a description of variables to be derived.*
[]

B. Participants:

1. *Describe the subjects who provided the original data and the population from which they were drawn.*

[]

Note: If you are receiving, accessing, or using data from a U.S. health care provider, the need for HIPAA review is likely. If you plan to bring identifiable health information from a foreign country to a U.S. covered entity (e.g., lab at the Hopkins SOM), HIPAA may be triggered. If either of these conditions is met, check “yes” to the HIPAA question in the PHIRST application.

2. *If you plan to analyze human specimens or genetic/genomic data, provide details about the source of those specimens and whether they were collected using an informed consent document. If yes, explain whether your proposed use is “consistent with” the scope of the original consent, if it potentially introduces new analyses beyond the scope of the original consent, and/or if it introduces new sensitive topics (HIV/STDs, mental health, addiction) or cultural/community issues that may be controversial.*

[]

3. *Explain whether (and how) you plan to return results to the participants either individually or as a group.*

[]

XII. Oversight Plan for Student-Initiated Studies:

- A. *For student-initiated studies, explain how the PI will monitor the student’s adherence to the IRB-approved research plan, such as communication frequency and form, training, reporting requirements, and anticipated time frame for the research. Describe who will have direct oversight of the student for international studies if the PI will not personally be located at the study site, and their qualifications.*

[]

B. *What is the data custody plan for student-initiated research? (Note: Students may not take identifiable information with them when they leave the institution.)*

[]

XIII. Creation of a Biospecimen Repository:

Explain the source of the biospecimens, if not described above, and what kinds of specimens will be retained over time. Clarify whether the specimens will be obtained specifically for repository purposes, or will be obtained as part of the core study and then retained in a repository.

A. *Describe where the biospecimens will be stored and who will be responsible for them.*

[]

B. *Describe how long the biospecimens will be stored, and what will happen at the end of that period.*

[]

C. *Explain whether the biospecimens will be shared with other investigators, inside and outside of JHU, how the decision to share will be made, and by whom. Include your plans, if any, for commercial use. Also explain how downstream use of the specimen will be managed, and what will happen to left-over specimens.*

[]

D. *Describe whether future research using the biospecimens will include specimen derivation and processing (cell lines, DNA/RNA, etc.), genomic analyses, or any other work which could increase risk to participants. Explain what additional protections will be provided to participants.*

[]

E. *If future research could yield unanticipated incidental findings (e.g., an unexpected finding with potential health importance that is not one of the aims of the study) for a participant, do you intend to disclose those findings to the study participant? Please explain your position.*

[]

F. *Explain whether the specimens will be identifiable, and if so, how they will be coded, who will have access to the code, and whether the biospecimens will be shared in linked (identifiable) form.*

[]

G. Explain whether the repository will have Certificate of Confidentiality protections.

[]

H. Explain whether a participant will be able to withdraw consent to use a biospecimen, and how the repository will handle a consent withdrawal request.

[]

I. Describe data and/or specimen use agreements that will be required of users.

Provide a copy of any usage agreement that you plan to execute with investigators who obtain biospecimens from you.

[]

XIV. Data Coordinating Center:

Complete if BSPH serves as the Data Coordinating Center.

A. How will the study procedures be developed?

[]

B. How will the study documents that require IRB approval at each local site be developed? Will there be some sort of steering or equivalent committee that will provide central review and approval of study documents, or will template consent forms, recruitment materials, data collection forms, etc. be developed by and provided to the local sites by the coordinating center without external review?

[]

C. Will each local clinical site be overseen by its own IRB with an FWA, or will a Single IRB review the study? State whether the coordinating center will collect IRB approvals and renewals from the clinical centers; if not, explain why.

[]

D. How will the coordinating center provide each local site with the most recent version of the protocol and other study documents? What will be the process for requesting that these updates be approved by local clinical center IRBs?

[]

E. What is the plan for collecting data, managing the data, and protecting the data at the coordinating center?

[]

F. What is the process for reporting and evaluating protocol events and deviations from the local sites? Who has overall responsibility for overseeing subject safety: the investigators at the recruitment site, the Coordinating Center, the Steering

Committee, or a Data and Safety Monitoring Board (DSMB)? Is there a DSMB that will evaluate these reports and provide summaries of safety information to all the reviewing IRBs, including the coordinating center IRB? Please note that if there is a DSMB for the overall study, then the coordinating center PI does not have to report to the coordinating center IRB each individual adverse event/problem event that is submitted by the local site PIs.

[]

G. *Some FDA regulated studies have different AE reporting criteria than that required by the IRB (IRB Policy No. 103.06). How will you reconcile the different requirements, and who is responsible for this reconciliation?*

[]

H. *Who is responsible for compliance with the study protocol and procedures and how will the compliance of the local sites be monitored and reviewed? How will issues with compliance be remedied?*

[]

XV. Drug Products, Vitamins, Food and Dietary Supplements:

Complete this section if your study involves a drug, botanical, food, dietary supplement or other product that will be applied, inhaled, ingested or otherwise absorbed by the study participants. If you will be administering drugs, please upload the product information.

A. *List the name(s) of the study product(s), and the manufacturer/source of each product.*

Name of Study Product	Manufacturer/Source
[]	[]

B. *List each study product by name and indicate its approved/not approved status.*

Approved by the FDA and Commercially Available	Approved by Another Gov't Entity (provide name)	Cleared for Use at Local Study Site

C. If your study product has an *Investigational New Drug (IND)* application through the U.S. Food and Drug Administration, provide the *IND* number, and the *Investigators Brochure*.

[]

Who will hold the IND?

[]

D. If your study product is a marketed drug, provide the package inserts or other product information. If the study product *WILL NOT* be used for its approved indication, dose, population, and route of administration, provide a detailed rationale justifying the off-label use of the study product.

[]

E. If the study product does not require FDA approval (e.g., dietary supplements, botanicals, products not subject to the U.S. FDA, etc.), provide safety information (as applicable) and a certificate of analysis.

[]

F. Explain who will be responsible for drug management and supply, labeling, dispensing, documentation and recordkeeping. Complete and upload into PHIRST the Drug Data Sheet available on the [[BSPH IRB Website](#)]

[]

G. What drug monitoring and/or regulatory oversight will be provided as part of the study? Please describe.

[]

XVI. Medical Devices:

Complete this section if your study will involve an approved or investigational medical device (**diagnostic**, non-significant risk, significant risk).

A. List the name(s) of the study product(s), the manufacturer/source of each product, and whether or not it is powered (electric, battery). Provide product information. If it is electric, upload documentation of clinical engineering approval or its equivalent from a local authority, to ensure that the device is in good

working order.

Name of Study Product	Manufacturer/Source	Powered?

B. List each study product by name and indicate its status as approved by a government authority or not approved.

Approved by the FDA and Commercially Available	Approved by Another Gov't Entity (provide name and approval information)	Not Approved

C. If your investigational device is Exempt from the FDA IDE regulations, explain which section of the code applies to your device and why it meets the criteria provided. If it is a **diagnostic device**, provide pre-clinical information about the sensitivity and specificity of the test and the anticipated failure rate. If you plan to provide the results to participants or their physicians, justify doing so, and explain how those results will validated (or not) against the current “gold standard”.

[]

D. If you believe the investigational device is not IDE exempt under 21CFR 812.2(c), but is a “Non-Significant Risk” device considered to have an approved IDE application, provide information from the manufacturer supporting that position.

[]

E. If you are using an investigational device that is a Significant Risk Device, provide the IDE number given by the FDA, or if not under FDA jurisdiction, explain why it is appropriate to use this device in this study. Provide a description of the device, and upload a picture or manufacturing schematics into PHIRST. Provide any other information relevant to a determination of its safety to be used for the purposes outlined in this research plan.

[]
